#### 13.4. Additional Assessments

[REDACTED]

[REDACTED]

[REDACTED]

[REDACTED]

- [REDACTED]
- [REDACTED]
- [REDACTED]

[REDACTED]

##### 13.4.2. ApoE Genotyping

Whole blood samples for deoxyribonucleic acid (DNA) ApoE genotyping will be collected from all subjects at the Screening Visit.

CONFIDENTIAL

The information contained herein may not be used, disclosed, or published without the written consent of Biogen MA Inc.

[REDACTED]

#### 13.4.4. Health Outcomes Assessments

The following assessments will be performed to evaluate the effect of aducanumab in subjects and caregivers:

- EQ-5D (SR)
- EQ-5D (IR-S)
- [REDACTED]
- mPDQ-20
- [REDACTED]

Some tests will require the informant/care partner to participate and answer questions regarding the subject's daily activities and cognitive capabilities.

The recommended order of administration of the clinical assessments is described in the Study Reference Guide.

CONFIDENTIAL

The information contained herein may not be used, disclosed, or published without the written consent of Biogen MA Inc.

## 14. SAFETY ASSESSMENTS

See Section 4.2 for the timing of assessments.

### 14.1. Clinical Safety Assessments

The following clinical assessments will be performed to evaluate the safety profile of aducanumab:

- AE and SAE monitoring.
- Physical examination, including height and weight.
- Neurological examination.
- Vital signs (body temperature, heart rate, SBP, DBP, and respiratory rate).
- 12-lead ECG.
- Brain MRI.
- Concomitant medication, therapy and procedure monitoring.
- MOCA (for ARIA monitoring and management).
- Columbia Suicide Severity Rating Scale.

### 14.2. Laboratory Safety Assessments

The following laboratory assessments will be performed to evaluate the safety profile of aducanumab

- Hematology: complete blood count with differential and platelet count, and absolute neutrophil count.
- Blood chemistry: total protein, albumin, creatinine, blood urea nitrogen, uric acid, bilirubin (total and direct), alkaline phosphatase, ALT, AST, lactate dehydrogenase, gamma-glutamyl-transferase, glucose, calcium, phosphorus, bicarbonate, chloride, sodium, and potassium.
- Urinalysis: color, specific gravity, pH, protein, glucose, blood, ketones, and microscopic examination (if abnormal).
- Serum and urine pregnancy test for women of childbearing potential only.
- Coagulation, virology (including HIV at the Investigator's discretion after consideration of risk factors), HbA1c, and alcohol/drug screen at Screening.

CONFIDENTIAL

The information contained herein may not be used, disclosed, or published without the written consent of Biogen MA Inc.

### **14.3. Immunogenicity Assessments**

Presence of serum anti-aducanumab will be determined using a validated assay. A standard 3-tier anti-drug antibody (ADA) approach will be used (i.e., Screening assay, confirmatory assay, and titration assay). Confirmed antidrug antibody-positive samples will be tested for the presence of anti-aducanumab neutralizing antibodies using a validated assay.

CONFIDENTIAL

The information contained herein may not be used, disclosed, or published without the written consent of  
Biogen MA Inc.

## **15. SAFETY DEFINITIONS, RECORDING, REPORTING, AND RESPONSIBILITIES**

Throughout the course of the study, every effort must be made to remain alert to possible AEs. If an AE occurs, the first concern should be for the safety of the subject. If necessary, appropriate medical intervention should be provided.

At the signing of the ICF, each subject or his/her legally authorized representative must be given the names and telephone numbers of study site staff for reporting AEs and medical emergencies.

### **15.1. Definitions**

#### **15.1.1. Adverse Event**

An AE is any untoward medical occurrence in a patient or clinical investigation subject administered a pharmaceutical product and that does not necessarily have a causal relationship with this treatment. An AE can therefore be any unfavorable and unintended sign (including an abnormal laboratory finding), symptom, or disease temporally associated with the use of a medicinal (investigational) product, whether or not related to the medicinal (investigational) product.

Determination of whether an abnormal laboratory value meets the definition of an AE will be made by the Investigator. Although abnormal laboratory values are typically not considered AEs, the following considerations may result in an abnormal laboratory value being considered an AE:

- A laboratory test result that meets the criteria for an SAE.
- A laboratory test result that requires the subject to receive specific corrective therapy.
- A laboratory abnormality that the Investigator considers to be clinically significant.

Pre-treatment, nonserious AEs that occur within 48 hours after receipt of a ligand will be captured by the sites on the AE form.

#### **15.1.2. Serious Adverse Event**

An SAE is any untoward medical occurrence that at any dose:

- Results in death.
- In the view of the Investigator, places the subject at immediate risk of death (a life-threatening event); however, this does not include an event that, had it occurred in a more severe form, might have caused death.
- Requires inpatient hospitalization or prolongation of existing hospitalization.
- Results in persistent or significant disability/incapacity.
- Results in a congenital anomaly/birth defect.

CONFIDENTIAL

The information contained herein may not be used, disclosed, or published without the written consent of  
Biogen MA Inc.

An SAE may also be any other medically important event that, in the opinion of the Investigator, may jeopardize the subject or may require intervention to prevent one of the other outcomes listed in the definition above. (Examples of such medical events include allergic bronchospasm requiring intensive treatment in an emergency room or convulsions occurring at home that do not require an inpatient hospitalization.)

### **15.1.3. Prescheduled or Elective Procedures or Routinely Scheduled Treatments**

A prescheduled or elective procedure or a routinely scheduled treatment will not be considered an SAE, even if the subject is hospitalized. The study site must document all of the following:

- The prescheduled or elective procedure or routinely scheduled treatment was scheduled (or was on a waiting list to be scheduled) prior to obtaining the subject's consent to participate in the study.
- The condition requiring the prescheduled or elective procedure or routinely scheduled treatment was present before and did not worsen or progress in the opinion of the Investigator between the subject's consent to participate in the study and the time of the procedure or treatment.
- The prescheduled or elective procedure or routinely scheduled treatment is the sole reason for the intervention or hospital admission.
  - If a subject is hospitalized due to local requirements for administration of the study treatment, the hospitalization should not be considered an SAE unless one of the requirements in Section 15.1.2 is met.

## **15.2. Safety Classifications**

### **15.2.1. Investigator Assessment of Events**

All events must be assessed to determine the following:

- If the event meets the criteria for an SAE as defined in Section 15.1.2.
- The relationship of the event to study treatment as defined in Section 15.2.2.
- The severity of the event as defined in Section 15.2.3.

CONFIDENTIAL

The information contained herein may not be used, disclosed, or published without the written consent of Biogen MA Inc.

### 15.2.2. Relationship of Events to Study Treatment

The following definitions should be considered when evaluating the relationship of AEs and SAEs to the study treatment.

Relationship of Event to Study Treatment	
Not related	An AE will be considered "not related" to the use of the investigational drug if there is not a reasonable possibility that the event has been caused by the product under investigation. Factors pointing toward this assessment include but are not limited to: the lack of reasonable temporal relationship between administration of the drug and the event, the presence of a biologically implausible relationship between the product and the AE, or the presence of a more likely alternative explanation for the AE.
Related	An AE will be considered "related" to the use of the investigational drug if there is a reasonable possibility that the event may have been caused by the product under investigation. Factors that point toward this assessment include but are not limited to: a positive rechallenge, a reasonable temporal sequence between administration of the drug and the event, a known response pattern of the suspected drug, improvement following discontinuation or dose reduction, a biologically plausible relationship between the drug and the AE, or a lack of an alternative explanation for the AE.

### 15.2.3. Severity of Events

The following definitions should be considered when evaluating the severity of AEs and SAEs:

Severity of Event	
Mild	Symptom(s) barely noticeable to subject or does not make subject uncomfortable; does not influence performance or functioning; prescription drug not ordinarily needed for relief of symptom(s) but may be given because of personality of subject.
Moderate	Symptom(s) of a sufficient severity to make subject uncomfortable; performance of daily activity is influenced; subject is able to continue in study; treatment for symptom(s) may be needed.
Severe	Symptom(s) cause severe discomfort; symptoms cause incapacitation or significant impact on subject's daily life; severity may cause cessation of treatment with study treatment; treatment for symptom(s) may be given and/or subject hospitalized.

### 15.2.4. Expectedness of Events

Expectedness of all AEs will be determined by Biogen according to the IB for aducanumab.

## 15.3. Monitoring and Recording Events

### 15.3.1. Adverse Events

Any AE experienced by the subject between the time of first dose of study treatment and the subject's final clinic visit (including FU visit) is to be recorded on the CRF, regardless of the severity of the event or its relationship to study treatment. Pre-treatment, nonserious AEs that occur within 48 hours after receipt of a ligand will be captured by the sites on the AE form.

CONFIDENTIAL

The information contained herein may not be used, disclosed, or published without the written consent of Biogen MA Inc.

### 15.3.2. Adverse Events of Special Interest

ARIA-E and ARIA-H are considered AEs of special interest and will be entered on the Adverse Event of Special Interest CRF within 72 hours following the receipt of abnormal MRI findings from the central MRI reader.

AE reporting for ARIA-E and ARIA-H will be based on the following centrally read MRI sequences: fluid attenuated inversion recovery/T2 for ARIA-E and T2\*/gradient echo for ARIA-H.

**If the event qualifies as an SAE an SAE form should be submitted per the guidelines in Section 15.3.4. Investigators should include a copy of the centrally read MRI report when submitting the SAE form to [REDACTED].**

### 15.3.3. Serious Adverse Events

Any SAE experienced by the subject between signing of the ICF and the subject's final clinic visit (including FU visit) will be recorded on an SAE form, regardless of the severity of the event or its relationship to study treatment. SAEs must be reported to Biogen (or designee) within 24 hours as described in Section 15.3.4. This also applies to SAEs that occur after administration of the ligand. FU information regarding an SAE also must be reported with 24 hours.

Events occurring after the subject's final clinic visit (including FU visit) should be reported to Biogen only if the Investigator considers the SAE related to study treatment.

Any SAE that is ongoing when the subject completes or discontinues the study will be followed by the Investigator until the event has resolved, stabilized, or returned to baseline status.

### 15.3.4. Immediate Reporting of Serious Adverse Events

In order to adhere to all applicable laws and regulations for reporting an SAE, the study site must formally notify [REDACTED] within 24 hours of the study site staff becoming aware of the SAE. It is the Investigator's responsibility to ensure that the SAE reporting information and procedures are used and followed appropriately.

#### Reporting Information for SAEs

Any SAE that occurs between the time that the subject has signed the ICF and the subject's final clinic visit (including FU visit) must be reported to [REDACTED] within 24 hours of the study site staff becoming aware of the event. Thereafter, the event should be reported only if the Investigator considers it related to study treatment.

A report ***must be submitted*** to [REDACTED] regardless of the following:

- Whether or not the subject has undergone study-related procedures
- Whether or not the subject has received study treatment
- The severity of the event

CONFIDENTIAL

The information contained herein may not be used, disclosed, or published without the written consent of Biogen MA Inc.

- The relationship of the event to study treatment

To report initial or FU information on an SAE, fax or email a completed SAE form. Refer to the Study Reference Guide for country-specific [REDACTED] fax numbers or email [REDACTED]

#### 15.3.4.1. Deaths

Death is an outcome of an event. The event that resulted in death should be recorded on the appropriate CRF. All causes of death must be reported as SAEs within 24 hours of the site becoming aware of the event. The Investigator should make every effort to obtain and send death certificates and autopsy reports to [REDACTED]. The term death should be reported as an SAE only if the cause of death is not known and cannot be determined.

#### 15.3.5. Suspected Unexpected Serious Adverse Reactions

Suspected unexpected serious adverse reactions (SUSARs) are SAEs that are unexpected and judged by the Investigator or Biogen to be related to the study treatment administered.

Appropriate personnel in Biogen Safety and Benefit Risk (SABR) will unblind SUSARs for the purpose of regulatory reporting. Biogen or designee will submit SUSARs (in blinded or unblinded fashion) to regulatory agencies according to local law. Biogen or designee will submit SUSARs to Investigators in a blinded fashion.

### 15.4. Procedures for Handling Special Situations

#### 15.4.1. Pregnancy

**Subjects should not become pregnant or impregnate their partners during the study and for 24 weeks after their last dose of study treatment.** If a female subject becomes pregnant, study treatment must be discontinued *immediately*.

The Investigator must report a pregnancy occurring in a female subject by faxing the appropriate form to [REDACTED] within 24 hours of the study site staff becoming aware of the pregnancy at the SAE reporting fax number provided in the study reference manual. The Investigator or study site staff must report the outcome of the pregnancy to [REDACTED].

Congenital abnormalities and birth defects in the offspring of male or female subjects should be reported as an SAE if conception occurred during the study treatment period.

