The total duration of study participation for each subject participating in the placebo-controlled period and the LTE period will be up to approximately 206 weeks, including a series of Screening visits within 8 weeks before administration of the first dose, a 76-week placebo-controlled treatment period, a 4-week FU period, a 100-week aducanumab dose-blind treatment period, and a safety FU period of approximately 18 weeks after the final dose. The FU period of 18 weeks is based on an estimated mean elimination half-life in humans of 16 to 24 days (mean approximately 20 days, based on results from the single ascending dose study [Study 221AD101]) and anticipated brain concentrations of aducanumab of less than one-third the  $EC_{50}$  (inhibitory concentration at 50% of the maximum observed biologic effect) for binding fibrillar amyloid at 8 weeks after the last dose.

During the placebo-controlled period, ApoE  $\epsilon$ 4 carriers will receive placebo, aducanumab 3 mg/kg, or aducanumab 6 mg/kg whereas ApoE  $\epsilon$ 4 non-carriers will receive placebo, aducanumab 6 mg/kg, or aducanumab 10 mg/kg. Aducanumab will be titrated for up to 6 doses prior to reaching the target dose as shown in [Table 7](#) and [Figure 1](#). Subjects who received

CONFIDENTIAL

The information contained herein may not be used, disclosed, or published without the written consent of Biogen MA Inc.

aducanumab in the placebo-controlled period and who enter the LTE period will receive the same dose of aducanumab that they received at the end of the placebo-controlled period (up to 6 mg/kg and 10 mg/kg in ApoE  $\epsilon$ 4 carriers and non-carriers, respectively). Subjects who received placebo during the placebo-controlled period and who enter the LTE period will be assigned to treatment based upon their ApoE  $\epsilon$ 4 carrier status in a 1:1 ratio (aducanumab low dose: aducanumab high dose); aducanumab will be titrated for up to 6 doses prior to reaching the target dose following the same schedule described for the placebo-controlled period.

See Section 5.3.2 for details of dosing scheme modification.

Individual dose adjustments may also be implemented to subjects who develop ARIA. See Section 7.2.1.

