## 8. SELECTION OF SUBJECTS

### 8.1. Inclusion Criteria

To be eligible to participate in this study, candidates must meet the following eligibility criteria at Screening or at the time point specified in the individual eligibility criterion listed:

1. Ability to understand the purpose and risks of the study and provide signed and dated informed consent and authorization to use confidential health information in accordance with national and local subject privacy regulations.
2. Aged 50 to 85 years old, inclusive, at the time of informed consent.
3. All women of childbearing potential and all men must practice highly effective contraception during the study and for 24 weeks after their last dose of study treatment. For further details of contraceptive requirements for this study, please refer to Section 15.5.
4. Must have at least 6 years of education or work experience to exclude mental deficits other than MCI or mild AD.
5. Must have a positive amyloid PET scan. Previously obtained PET scan (within 12 months of Screening) is permissible for subjects not participating in the amyloid PET cohort. Previous PET scan images must be submitted to the central imaging vendor to confirm study inclusion criteria are met.
6. Must meet all of the following clinical criteria for MCI due to AD or mild AD according to NIA-AA criteria [Albert 2011; McKhann 2011], and must have:
  - A CDR-Global Score of 0.5.
  - An RBANS score of 85 or lower indicative of objective cognitive impairment (based upon the Delayed Memory Index (DMI) score).
  - An MMSE score between 24 and 30 (inclusive).
7. Apart from a clinical diagnosis of early AD, the subject must be in good health as determined by the Investigator, based on medical history and Screening assessments.
8. Must consent to apolipoprotein E (Apo E) genotyping.
9. Has one informant/care partner who, in the Investigator's judgment, has frequent and sufficient contact with the subject as to be able to provide accurate information about the subject's cognitive and functional abilities. The informant/care partner must minimally be available by phone to provide information to the Investigator and study staff about the subject and agrees to attend in person clinic visits that require partner input for scale completion. An informant/care partner should be available for the duration of the study, and the use of the same informant/care partner for the duration of the study is encouraged.

CONFIDENTIAL

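### Section 15.4.1 ties SAE reporting of birth defects to conception in the treatment period, a narrower window than the 24 weeks after the last dose in which the same section says conception must be avoided

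*Protocol*

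**What the plan says.** References are to protocol v3.0, the latest version whose safety-reporting text is supplied. The birth-defect sentence reads the same in v1.0 and v2.0. The supplied v4.0 text stops in the schedule tables, so its Section 15.4.1 appears only as a contents entry.

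- **Avoidance window.** Section 15.4.1: "Subjects should not become pregnant or impregnate their partners during the study and for 24 weeks after their last dose of study treatment". Inclusion criterion 3 in Section 8.1 uses the same limit, asking for highly effective "contraception during the study and for 24 weeks after their last dose of study treatment".
- **Reporting trigger.** Two paragraphs later, Section 15.4.1 turns to malformations in the children of subjects of either sex. The rule is that these "should be reported as an SAE if conception occurred during the study treatment period".
- **Treatment period.** Sections 7.1 and 7.3 give a 76-week treatment period followed by a separate follow-up of 18 weeks. Section 7.3.3 puts the last visit at Week 94, or at Week 198 for subjects in the extension.
- **Elimination.** Section 7.1 gives an "estimated mean elimination half-life in humans of 16 to 24 days", with a mean of about 20 days.
- **General SAE rules.** Section 15.1.2 counts a congenital anomaly or birth defect as an SAE, with no limit on the date of conception. Section 15.3.3 covers SAEs experienced by the subject from consent to the final clinic visit, whatever their relationship to treatment. Later events "should be reported to Biogen only if the Investigator considers the SAE related to study treatment".
- **Pregnancy reports.** Sections 15.4.1 and 15.6.1 require reports of pregnancies, and of their outcomes, in female subjects. There is no matching duty for partners of male subjects.

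**The concern.** One section sets two windows for the same risk. By asking subjects to avoid conception for 24 weeks after dosing, the protocol treats those weeks as a period of possible harm. The sentence that turns a birth defect into a reportable SAE does not reach into them.

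What is at stake is whether rare offspring outcomes, from conceptions the protocol itself regards as at risk, reach the safety database by rule or only by discretion. The question matters most for male subjects. The birth-defect sentence is the only reporting rule that names their offspring, and no pregnancy report stands behind it.

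**Working it through.** **1. The plan's own figures.** The last placebo-controlled infusion is at Week 76 (Day 533) and the follow-up visit is at Week 94 (Day 659). 94 − 76 = 18 weeks, and 659 − 533 = 126 days = 18 weeks. For the extension, 198 − 180 = 18 weeks. The midpoint of the half-life range is (16 + 24)/2 = 20 days. All agree with the text.

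**2. Size of the mismatch.** The avoidance window ends 24 weeks (168 days) after the last dose.

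- If the treatment period ends at the last dose, as Sections 7.1 and 7.3 use the term, the uncovered window is 24 − 0 = 24 weeks.
- If it were read to include the 18-week follow-up, 24 − 18 = 6 weeks would still be uncovered.

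Section 15.4.1 does not define the term. The mismatch remains on either reading.

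**3. Drug remaining after the last dose.** Assuming first-order elimination, the fraction remaining is 2^(−t/h), with t in days and h the half-life. For example, at 8 weeks with h = 20: 2^(−56/20) = 2^(−2.8) = 14%.

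| Weeks after last dose | h = 16 days | h = 20 days | h = 24 days |
|---|---|---|---|
| 4 | 30% | 38% | 45% |
| 8 | 9% | 14% | 20% |
| 12 | 2.6% | 5.4% | 8.8% |
| 18 | 0.4% | 1.3% | 2.6% |
| 24 | 0.07% | 0.3% | 0.8% |

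Five half-lives end at 5h/7 = 11.4, 14.3 and 17.1 weeks. The 24-week limit is 168/h = 10.5, 8.4 and 7.0 half-lives. The half-life therefore shows appreciable drug in the early part of the uncovered window and almost none at its end.

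**4. Other routes for a birth defect from a conception in the uncovered window.**

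| Route | Female subject | Partner of male subject |
|---|---|---|
| Birth-defect sentence, 15.4.1 | Outside the trigger | Outside the trigger |
| Pregnancy and outcome report, 15.4.1 and 15.6.1 | Required, but not as an SAE report | None stated |
| General SAE rule up to the final visit, 15.3.3 | Applies if the birth precedes the visit, though worded for events in the subject | Doubtful, for the same wording |
| General SAE rule after the final visit, 15.3.3 | Only if judged related | Only if judged related |

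For a subject who completes treatment, the final visit is 18 weeks after the last dose. Assuming that a pregnancy carried to term lasts longer than 18 weeks, a birth conceived after the last dose falls after that visit. The last row then governs.

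**The case against.** The strongest reply is that the sentence excludes nothing. It says *if*, not *only if*, and can be read as an instruction that extends SAE reporting to offspring. Section 15.1.2 already makes a birth defect an SAE whatever the date of conception. For female subjects, the pregnancy must be reported within 24 hours of the site learning of it, and its outcome must follow, with no limit by conception date or causality. Subjects who stop treatment early stay in the study, so their final visit can be much later than 18 weeks after the last dose, and a birth may precede it.

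All of this stands, and it rules out two stronger readings. A reader might infer that offspring outcomes from conceptions after dosing are excluded by rule from the safety database. The text does not say so, and for female subjects the outcome report contradicts it. A reader might also infer that the half-life itself puts drug-exposed conceptions out to 24 weeks. It does not: less than 1% remains by then, and the 24-week limit comes from the contraception window alone. Nor does the serum level in a male subject show exposure of the embryo in his partner, on which the documents give no figure.

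The reply does not remove the mismatch. Section 15.3.3 is worded for events in the subject, its unconditional part ends at the final visit, and partners of male subjects have no pregnancy report.

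**Conclusion.** The inconsistency holds, at low severity. The stated trigger falls short of the section's own avoidance window by 24 weeks on the natural reading, and by 6 weeks on the most generous one. In the first 8 weeks of that gap, the drug remaining falls from its level at the last dose to 9-20% of it. The practical gap lies mainly with partners of male subjects, where nothing backs up the birth-defect sentence and reporting after the final visit depends on causality opinion.

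The conclusion rests on three assumptions: that treatment period means the dosing weeks, that elimination is first-order at the stated half-lives, and that the v3.0 wording carries over to v4.0, which cannot be confirmed here. Few events are expected at ages 50 to 85. Power, Type I error and the primary analysis are not affected.

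**What to change.** First check whether v4.0 keeps the sentence. If it does, reconcile the birth-defect sentence in Section 15.4.1 with the avoidance window stated in the same section, so that both use the same end point. Add that birth defects the site learns of from conceptions in that window are reported as SAEs after the final clinic visit, regardless of the Investigator's causality opinion, and point to this from Section 15.3.3.

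The cost is a few words in two sections, matching instructions for the SAE form, and a small added reporting load. Limiting the duty to events the site learns of avoids any new scheme for tracking partners. The price is that some partner outcomes will still go unseen.
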